8.2 Setting

Patients followed by the ambulatory of neuromuscular disorders of Centro Dino Ferrari, Padiglione Monteggia of Fondazione IRCCS Ca' Granda Ospedale Maggiore Policlinico (Unit of Neurology), will be recruited during the ordinary follow up routine or will be reached out to participate to this study. Furthermore, thank to the sponsorship of Gruppo familiari beta sarcoglicanopatie (GFB), more patients that are in the network of this association will be reached out from the PI of the study and eventually included. Data will be provided by patients themselves during the visit at the room number 17 of Padiglione Monteggia of Fondazione IRCCS Ca' Granda Ospedale Maggiore Policlinico (Unit of Neurology). If the patients won't be able to move and will be interested in participating to the study a collaborator of the main researcher will reach the patients at his residence to recruit him. Main source of data will be the clinical chart of the patient and all his clinical documents assessing any operation, ascertain, visits performer through the years until this moment. Main centre will be the Fondazione IRCCS Ca' Granda Ospedale Maggiore Policlinico (Unit of Neurology). Data collection will last six months and later data will be studied.

8.2.1 Study population

Studied population. The association GFB (GRUPPO FAMILIARI BETA-SARCOGLICANOPATIE) is a group of families of patients affected by beta-sarcoglycanopathy and other muscular dystrophies. This association has been created by few families resident in Lombardia and now it includes people from all over Italy. The study will be sponsored by GFB that will inform its associated about this study. Patients interested in participating to the study will reach out the PI of the study to be eventually included.

Furthermore, patients affected by LGMD 2E followed at the Fondazione IRCCS Ca' Granda Ospedale Maggiore Policlinico (Unit of Neurology) and that have previously signed an informed consent for the use of their data for scientific research will be included. Data from this second group of patients will already be available in databases created in our hospital for previous scientific researches.

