QMT= Quantitative Muscle Testing
RM = Magnetic Resonance
RX= radiography
VIT D= Vitamin D
VR= Residual Volume

3. Responsibility (role of the study promoter and of researchers)

Main researcher: [name] Collaborators: [name], graduated with [name] and now attending the first year of school in medical genetics at the Fondazione IRCCS Cà Granda, Ospedale Maggiore Policlinico. She will collect clinical charts and report clinical data to analyze in a excel file that will be used for the statistics. [name], Director of the Neuromuscular and rare Disease Unit

4. Emendamenti ed altre modifiche al protocollo Not relevant.

5. Timelines Planning: start of data collection: June 2020. End of data collection: September 2020
Final report: December 2020

6. Rational and background

LGMD2E is a rare type of a hereditary muscular dystrophy transmitted in an autosomic recessive manner. This disease is determined by the presence of mutations involving the Beta Sarcoglycan gene, coding for a protein which is involved in the stabilization of the glycoprotein complex

associated to dystrophin (1). The main role of beta Sarcoglycan only partly explains the severity of the clinical phenotype reported in these patients compared with other LGMD (2). LGMD 2E debuts in early childhood, involving skeletal muscles with a progressive centripetal trend that in last stages affects also respiratory and cardiac muscles (3). The early onset and the severity of the disease affecting cardiopulmonary apparatus, make this disease very close to the more famous and studied Duchenne Muscular Dystrophy (4). More than 60% of LGMD 2E patients suffer from heart failure (5), not less common is the involvement of respiratory system which insufficiency represents the main cause of death in these patients (6). Unfortunately, because of its rareness, literature is poor of data about this disorder and no natural history study have ever been reported until now. Lacking similar studies, therapeutical and clinical management is not easy and often based on studies investigating other subtypes of muscular dystrophies, often more benign.

Furthermore, we have little knowledge about possible genotype-phenotype correlations for this disease (7). We do believe that a natural history study might help us to improve our knowledge of this condition's evolution, leading to the design of specific guidelines for the follow up of these patients, both under the therapeutical and clinical point of view.

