8.2.3 Exclusion criteria

Th lacking subscription of informed consent and or the lack of genetic diagnosis represent the only exclusion criteria.

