8.5 Cohort dimension

Expected cohort dimension is of 33 patients that is the number of patients followed at the Neurological Unit in the last 10 years. Statistical analysis will be based on generalized linear regression models, suitable both for continuous variables both for independent ones. Variables with a nonlinear distribution will be used only in logarithmic scale. Only data corresponding to yearly visit (at least two data in two years) will be used for the linear correlation analysis and in multivariate correlation models. Furthermore, to verify the accuracy of clinical variables in

describing the evolution of the dystrophy, variables will be coupled and compared by a bivariate analysis.

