8.7 Data analysis

Analysis will be performed using generalized linear regression models suitable both for continuous variables both for independent ones. Variables with a nonlinear distribution will be transformed in logarithmic scale before the analysis to be performed. For any analysis data will be divided according to the age of the patient at the moment of the evaluation. Data will be analyzed with linear correlation both compared to the variable age both in bivariate models and multivariate models. Results obtained will be adjusted for confounding factors not related to muscular dystrophy.

Data of included patients will be globally studied and divided in two groups homogeneous for genotype.

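### Affected siblings with the same genotype may be enrolled, yet the protocol neither records nor accounts for family membership, so standard errors for the genotype comparison may be too small

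*Protocol*

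**What the plan says.** Section 6 describes the disease as "transmitted in an autosomic recessive manner". Section 8.2.1 gives two sources of patients. One is a families' association, which "is a group of families of patients affected by beta-sarcoglycanopathy and other muscular dystrophies"; the other is the hospital's own "patients affected by LGMD 2E followed at the Fondazione IRCCS Ca' Granda Ospedale Maggiore Policlinico (Unit of Neurology"). Section 8.2.3 states that missing consent and "the lack of genetic diagnosis represent the only exclusion criteria", so nothing limits enrolment to one patient per family.

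Section 8.1.1 lists the correlation between phenotype and genotype among the primary endpoints. For the analysis, section 8.7 says "Analysis will be performed using generalized linear regression models suitable both for continuous variables both for independent ones", and that data will also be "divided in two groups homogeneous for genotype". Adjustment is confined to confounders unrelated to the dystrophy. The data form in section 8.3 opens with a pseudonymised name, sex and age and continues with diagnostic, clinical and treatment items. It has no field for family. No section mentions relatedness or clustering.

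**The concern.** In a recessive disorder, two affected full siblings have normally inherited the same allele from each parent. They share the causal genotype and are likely to share environment and care. Their outcomes, such as the age at loss of ambulation defined in section 8.4, may therefore resemble each other more than those of unrelated patients with the same class of mutation.

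The genotype comparison is where this does most harm. Genotype is constant within a sibling pair, so any positive sibling correlation lies entirely inside one genotype group. A regression that counts the siblings as two separate pieces of evidence then gives a standard error that is too small. A model for repeated yearly values within a patient would not cure this, because family is a level above patient. What is at stake is overstated evidence for a genotype-phenotype correlation, in a cohort where each family carries a lot of weight.

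**Working it through.** **Plan's own figure.** Section 8.5 says "Expected cohort dimension is of 33 patients that is the number of patients followed at the Neurological Unit in the last 10 years". This is a head count. No significance level, power, effect size or standard deviation accompanies it, so there is no calculation to reproduce. It serves here only as the sample size.

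**Inputs from the protocol.** N = 33 (8.5); two genotype groups (8.7); no restriction on relatives (8.2.3).

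**Assumptions not in the protocol.** Number of sibling pairs p = 0 to 10; residual sibling correlation r = 0.3 to 0.8 (that is, after age and genotype group are taken into account); two-sided nominal level 0.05; pairs spread evenly over the two groups.

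**Formulas.** Each pair is a cluster of size 2 and every other patient a cluster of size 1:

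- Sum of squared cluster sizes / N = (4p + 33 − 2p) / 33 = 1 + 2p/33
- Design effect D = 1 + (2p/33) × r
- Standard error factor = √D
- Effective sample size = 33 / D
- Actual error rate of the unadjusted test = 2 × [1 − Φ(1.96 / √D)]

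**Worked ends of the range.**

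- p = 2, r = 0.3: D = 1 + (4/33)(0.3) = 1.036; √D = 1.018; effective n = 31.8; error rate 5.4%.
- p = 10, r = 0.8: D = 1 + (20/33)(0.8) = 1.485; √D = 1.219; effective n = 22.2; error rate 10.8%.

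**Range.**

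| Sibling pairs | Increase in SE (r = 0.3 to 0.8) | Effective n | Actual error rate |
|---|---|---|---|
| 0 | none | 33.0 | 5.0% |
| 2 | 2% to 5% | 31.8 to 30.1 | 5.4% to 6.1% |
| 4 | 4% to 9% | 30.8 to 27.6 | 5.8% to 7.3% |
| 6 | 5% to 14% | 29.8 to 25.6 | 6.3% to 8.5% |
| 10 | 9% to 22% | 27.9 to 22.2 | 7.1% to 10.8% |

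**Simulation check.** 20,000 two-sample t-tests per setting, with groups of 16 and 17 (an assumed split), gave 5.0% to 5.1% with no pairs, 5.5% for 2 pairs at r = 0.3, 7.1% for 6 pairs at r = 0.5, and 11.2% for 10 pairs at r = 0.8. Formula and simulation agree to within about half a percentage point.

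**The case against.** The strongest reply has four parts.

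**The document asserts neither siblings nor independence.** A reader might infer that recruiting through the association will bring in siblings, and that the plan treats patients as independent. The text supports neither as a statement. A group of families may have one affected member each, the association also covers other dystrophies, and the 33 is the clinic's count, not the association's. The word independent in sections 8.5 and 8.7 describes variables, not patients. This part stands, and the point is conditional for that reason.

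**Model detail belongs in the SAP.** A random effect or a clustered variance can properly be left to an SAP that is not shown. But section 8.3 itself lists the data to be extracted, and without a family code an SAP has nothing in the listed data to cluster on. Relatedness might be reconstructed through the separate decoding file described in sections 8.3 and 8.6, but only by going back to patient identities. That shows the remedy is cheap; it does not show that the plan provides it.

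**The size is assumed.** It is. Neither the pair count nor the correlation comes from the protocol, and the protocol sets no significance level for this comparison. The upper end places 20 of the 33 patients in sibling pairs, for which the protocol offers no evidence. At the lower end the effect is of little practical importance.

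**The study is descriptive and admits its small size.** Section 8.9 warns that significance may not be reached and that analyses may not be trustworthy if few patients take part. That concerns too little evidence. Unrecognised clustering works the other way, making the evidence look stronger than it is.

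**Conclusion.** The point holds in conditional form. Recessive inheritance, a family-based recruitment route and the absence of any limit on relatives make it possible that affected siblings enter. The listed data and the named models do not deal with that. If siblings enter and their outcomes are positively correlated, the direction is clear: standard errors for the genotype comparison are too small.

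The size cannot be determined from the protocol. It is nil with no sibling pairs, and lies between the ends of the range worked out above for 2 to 10 pairs. It does not follow that the planned genotype result will be wrong, only that its precision may be overstated by an amount the listed data would not let anyone assess. This is a modest improvement to the plan, not a flaw that undermines the study.

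**What to change.** Add a pseudonymised family code to the data form in section 8.3, and report how many patients are related and in how many families.

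If any are related, use standard errors clustered by family in the genotype analyses and in those of the milestone ages in section 8.4. A small-sample correction is needed: with 2 to 10 pairs there would be only 31 down to 23 families (33 − p), too few to rely on uncorrected cluster-robust errors. A family random effect is an alternative, with patient nested in family for the yearly data, though with few pairs its variance will be estimated imprecisely. Add a sensitivity analysis with one patient per family.

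The cost is one column at chart review and slightly wider intervals. If no patients are related, the analysis is unchanged and the report can say so.

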8.2.2 Inclusion criteria

Will be included only those patients, both adults and minors, that have a genetical diagnosis of LGMD 2E and that will sign the specific informed consent for data management.

8.2.3 Exclusion criteria

Th lacking subscription of informed consent and or the lack of genetic diagnosis represent the only exclusion criteria.

8.2.4 Patient participation

Patients might be asked to give to their physician their clinical charts in order to evaluate the visits and investigations performed through the years, also in other hospitals.

8.3 Variables

Will be extract from the clinical charts of these patients, after the sign of the informed consent for the data management, only retrospective data (therefore all those data older than the day of the recruiting visit).

These data will be reported in a excel file specifically created. On this file data will be anonymized through a patient identification code that will be decrypted in another separate file. For this file will be considered the following data:

a) Dati anagrafici:

1. Anonymized name
2. Sex
3. Age

Form 2- DIAGNOSIS:

- 1) Age at onset
- a) clinical presentation
- b) clinical progression
- 2) CK at onset
- 3) EMG

4) Biopsy:

- a) Histology
- b) Immunohistochemistry
- c) Western Blot

5) Genetic:

- a) In frame del/dupl
- b) Out of frame del/dupl
- c) Missense
- d) Nonsense

Form 3- CLINICAL DATA AND TREATMENTS:

Hospitalization: Data – Cause – Frequency* Surgery: Data – Complications* Fractures: Data – Frequency – Location* Fell: Data – Frequency* Emergency Room Accesses: Data – Cause*

APPARATUS

Skeletal-Muscle

1) Clinical tests:

NSAA* MFM* QMT* Brook Scale* Egen Klassifikation* Barthel Index* Walton and Gardner* & Medwin GSGC* Grip Strength (quantitative)* Handheld Dynamometry* Performance of the Upper Limb Module for DMD 2.0* 10m Walk: 1- normal, 2- slightly impaired- 3 moderately impaired- 4- impaired- 5 with device - 6 not walking but stands- 7 wheelchair 6MWT* time to rise from the floor* Climb 4 stairs (1 no help - 2 one hand on the leg – 3 two hands on the legs - 4 stand with help -5 Handrail - 6 hardly climbs- 7 Not able). 10m Run

Time to rise from a chair (1 Normal - 2 with difficulties -3* helping with one hand - 4 Helping with two hands - 5 other helps - 6 Impossible). Time to stand from the floor (1 Normal - 2 first rise the pelvis and then one hand on the floor - 3 First rise the pelvis and then two hands on the floor - 4 One hand on the leg - 5 Two hands on the legs - 6 Other help - 7 Impossible).

Neuromuscular evaluation (date): maximal voluntary strength: bilateral knees extension, Isometric contraction test*, bilateral knee flexion, Workspace volume

2) Exams:

CK* Muscular RMN

3) Symptoms:

Loss of independent ambulation* Calf hypertrophy (Unilateral/Bilateral, if bilateral → Symmetrical/Asymmetrical)* Calf atrophy: Unilateral/Bilateral, if bilateral → Symmetrical/Asymmetrical)* Tendon contractures* Scoliosis Scapular winging* Tiptoe gait pattern* Muscle pain* Muscular trophism* Muscular weakness (Symmetrical/Asymmetrical - Proximal/Distal - Progression: chronic/acute)* Muscle contractures (Unilateral/Bilateral - site*

Cramps: Severity – Frequency)* Clubfoot (Unilateral/Bilateral)* Spine anomalies* Ability to walk on toes* Fasciculations* Percussion induced muscular contractions* Macroglossia (yes/no)* Dysphagia(yes/no, Data onset, Progression chronic/acute, Severity-> light/moderate/severe, frequent aspirations:yes/no)

4) Muscles involved: shoulder* arms* forearms* hand* spine* pelvic muscles* thigh* leg* feet

5) Wheelchair: yes/no; if yes → changed through the years – still using yes/no – how long*-other ambulatory devices yes/no; if yes → name → still using yes/no – how long – has it been changed through the years?

6) Deambulation and motility: general comments* Electromyography*

Cardiovascular

1) Evaluations (data): general conditions: using devices to support heart function (eg. pacemakers, ICD, etc.) - name* still using? – How long? - has it been changed through the years?

2) Conduction system anomalies:

EKG * Holter EKG* Echocardiogram* events monitoring*

3)Cardiomyopathy* Heart RM*

4) Symptoms: basal rattling* Oedemas* slopes edemas * Holter* Echocardiogram: Description* FE* Left ventricle telediastolic Volume* Left ventricle telediastolic diameter* Ahythmies* Coronaropathy* Valve* Pulmonary hypertension* Palpitations* Syncope* almost syncope*

Respiratory

1) Evaluations (data):

2) Respiratory support: Invasive/ Noninvasive* Cough assist* Cough peak* Overnight BiPAP * Other*

3) Respiratory status* Pulsoxymetry/polysomnography (mean SpO2 - SpO2 minimal - FC mean - AHI – ODI – %* MVV – MIP – MEP. Dispnoea: supine position– stress induced – at rest*

4) Quality of sleep: daily somnolence* not restorative sleep* frequent overnight awakening* morning headaches* daily fatigue*

Laboratory Tests

1)Imaging tests (data): RX thorax* RX spine* RM muscle*

2) Blood tests: Glucose* Proteins* Hemoglobin* White blood cells* Neutrophils *INR* RATIO* CPK* LDH* Amilase* Cistatine C* AST * ALT * ALP * GGT * Bilirubin total/direct/ indirect* Creatinine* Electrolytes (Sodium – Potassium - Clorum – Calcium total/ionized)* Urine (macroscopic view - blood (Yes/No) – anomalies)*

3) Bone status: MOC - PTH pg/mL - VIT D1,25 pmol/L-VIT D 25 nmol/L*

4)Glycemic state: Insuline - Hb1aC* Pro BNP*

Autoimmune disease

Name*

Treatment*

Therapy

1) Name - posology – data – rationale

2) Prescriptions*

3) Pain therapy*

4) Steroids*

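### The 8.3 form as shown has no height or weight, so for size-dependent measures in growth years the planned correlation with age cannot separate growth from disease

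*Protocol*

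**What the plan says.** **Who is in the cohort.** Protocol 8.2.2 admits "both adults and minors, that have a genetical diagnosis of LGMD 2E", with no age limit. Section 6 places onset in early childhood, and 8.2 draws on clinical documents accumulated over the years. Charts of patients who are now adults may therefore also hold childhood measurements.

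**What is extracted.** Section 8.3 introduces its list with "For this file will be considered the following data". The demographic block holds three items: "Anonymized name", sex and age. Further down are measures that depend on body size: "Grip Strength (quantitative)* Handheld Dynamometry", maximal voluntary strength and 6MWT; "Left ventricle telediastolic Volume* Left ventricle telediastolic diameter"; and cough peak, MVV, MIP and MEP. No height, weight, BMI or body surface area appears anywhere in the list as shown, and no scale is stated for these measures.

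**How it is analysed.** Section 8.7 says: "Data will be analyzed with linear correlation both compared to the variable age both in bivariate models and multivariate models". Section 8.7.1 uses the distribution over age to look for correlation with progression, as the analysis of the primary endpoints. Two sentences in 8.7 bear on the problem: "For any analysis data will be divided according to the age of the patient at the moment of the evaluation" and "Results obtained will be adjusted for confounding factors not related to muscular dystrophy".

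**The concern.** In a growing child, age and body size rise together. A healthy ventricle gets larger and healthy muscle gets stronger. If a size-dependent measure is correlated with age over growth years without standardisation, the slope mixes growth and disease. The two directions differ:

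- Ventricular volume and diameter rise with growth, which can look like progressive dilatation.
- Strength, respiratory pressures and cough peak also rise with growth, which can offset and hide an early decline.

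The study exists to pick the variables that best track evolution (7, 8.1.1) and possibly to name examinations that are of no use (8.7.2). A mixed slope can rank a ventricular dimension too high and a strength or respiratory measure too low. An analysis plan alone could not repair this, because it cannot index values to measurements that the form does not collect.

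**Working it through.** **1. Do the existing rules cover it?**

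- *Division by age (8.7).* No cut-points and no split between growing and adult patients are given. An adult-only band would be free of growth. Within any band of minors, age still carries growth.
- *Confounder adjustment (8.7).* No factor is named. Body size fits the description, but the listed fields give only sex and age to adjust with. Age is already the regressor, so adjusting for it cannot separate growth from disease.
- *Log transformation (8.5, 8.7).* This turns a growth multiplier into an additive trend and does not remove it.
- *Normal ranges (8.8).* These are used to check data reliability, not to standardise values for analysis.

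**2. Size in one growing patient (illustration).** The protocol gives no body sizes. Assumptions: linear heart dimensions scale with body surface area (BSA) to the power 0.45 to 0.5, and volume scales in proportion to BSA.

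- BSA 0.7 to 1.7 m2, diameter: (1.7/0.7)^0.45 − 1 = 0.49; (1.7/0.7)^0.5 − 1 = 0.56. Volume: 1.7/0.7 − 1 = 1.43.
- BSA 0.9 to 1.7 m2, diameter: (1.7/0.9)^0.45 − 1 = 0.33; (1.7/0.9)^0.5 − 1 = 0.37. Volume: 1.7/0.9 − 1 = 0.89.

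These are rises with no disease at all.

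**3. Size in a correlation with age at n = 33 (illustration).** Section 8.5 gives 33 as the number of patients followed over ten years. It is a head count with no alpha, power or effect size, so there is no planned figure to reproduce. At an assumed two-sided 0.05, Fisher's z gives:

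- smallest significant r: tanh(1.96/√30) = 0.34
- r with 80% power: tanh((1.96 + 0.84)/√30) = 0.47

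A simulation used 3,000 runs per setting, one value per patient and the Pearson correlation of log(value) with age. All inputs are assumed: ages uniform; growth linear from age 5 to 18 by a factor f, then flat; residual SD on the log scale (about the CV) as shown.

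*Growth only, no disease: percentage of runs with a significant correlation*

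| f | CV | ages 5–25 | ages 5–40 |
|---|---|---|---|
| 1.25 | 10% | 95.1 | 74.4 |
| 1.25 | 20% | 46.5 | 29.5 |
| 1.25 | 30% | 25.9 | 15.6 |
| 1.5 | 10% | 100.0 | 96.9 |
| 1.5 | 20% | 90.4 | 64.0 |
| 1.5 | 30% | 61.6 | 37.2 |
| 2.0 | 10% | 100.0 | 99.5 |
| 2.0 | 20% | 99.7 | 92.2 |
| 2.0 | 30% | 93.7 | 72.7 |

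With growth divided out, the rate is 4.0% to 6.3% in every setting.

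*True decline, multiplied by exp(−loss × (age − 5)), ages 5–25, CV 30%: percentage of runs that detect the decline*

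| loss per year | f | unstandardised | growth divided out |
|---|---|---|---|
| 2% | 1.5 | 1.8 | 55.2 |
| 2% | 2.0 | 0.1 | 55.6 |
| 2% | 3.0 | 0.0 | 56.2 |
| 3% | 1.5 | 13.7 | 88.3 |
| 3% | 2.0 | 0.7 | 87.5 |
| 3% | 3.0 | 0.0 | 87.4 |
| 5% | 1.5 | 83.4 | 99.8 |
| 5% | 2.0 | 32.8 | 99.8 |
| 5% | 3.0 | 1.3 | 100.0 |

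The last column divides by the exact growth factor, which real indexing only approximates. The harm also depends on the setting: a fast decline with modest growth is still found in most runs.

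**The case against.** The other side has several sound points, and they limit how far the finding goes.

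- *A reader might infer that raw values are certain to be analysed.* The protocol never says so. It names tests and gives no scale. Some charts may already report indexed or percent-predicted values, and a stray percent sign stands just before MVV in a damaged part of the list. What stands is that nothing requires standardised values, so absolute and standardised values could be mixed.
- *A reader might infer that children and adults are simply pooled.* The division by age in 8.7 exists, and its bands could be left to an analysis plan. Separating adults would protect the adult results. It would not remove growth from the minors' results.
- *A reader might infer that the loss is irreversible.* The study is retrospective, and each record can be traced to its patient through the separate key file (8.3, 8.6). Any height or weight in the charts could be extracted later, at the cost of a second pass.
- *A reader might infer that the whole primary analysis and the cardiopulmonary objective are biased.* Only size-dependent measures are concerned. Ejection fraction, SpO2, AHI, the ordinal motor scales and the three clinical outcomes in 8.4, which are ages, need no indexing.
- *The list may be incomplete as shown.* The abbreviation list defines residual volume, which the form as shown does not contain, and the asterisks have no visible legend. The finding therefore concerns the form as shown.
- *The magnitude is assumed.* The protocol gives no age distribution. If most dated measurements come from adults, the effect could be small.

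**Conclusion.** The point holds in a limited form. For left ventricular end-diastolic volume and diameter, cough peak, MVV, MIP, MEP, grip strength, dynamometry, maximal strength and 6MWT, section 8.3 as shown neither collects body size nor asks for standardised values. The analysis in 8.7 and 8.7.1 nevertheless reads their relation with age as progression. In records from growth years, growth can pass for progression or can mask decline, and the adjustment promised in 8.7 cannot be carried out for body size with the listed fields.

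The size of the bias in this cohort cannot be stated, because it depends on the unknown share of childhood records. Under the assumed inputs, growth alone gave a significant correlation with age in 16% to 100% of runs, against about 5% when growth was divided out. A true loss of 2% to 3% a year was found in 0% to 14% of runs, against 55% to 88%. These figures show that the effect can matter at n = 33; they are not estimates for this study. The change should be made.

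**What to change.** 1. In 8.3, add height (or a length surrogate such as ulna length or arm span, where the chart gives one) and weight at each dated evaluation.
2. For each size-dependent measure, record any indexed, z-score or percent-predicted value already in the report, with its reference, and state the scale of every value entered.
3. In 8.7, use standardised values for these measures in the age analyses: ventricular volume and diameter indexed to body surface area or as z-scores, and the other listed measures as percent predicted or z-scores where a reference exists.
4. Where body size is missing for a value taken while the patient was a minor, and no standardised value is reported, leave that value out of the pooled age correlation and report it descriptively.

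**Cost.** Two more fields from charts that are being read anyway, plus a conversion step. Some older records will lack height or weight, and height may be unreliable in patients with scoliosis or contractures. Some childhood values will therefore drop out of these analyses, which is a real loss in a cohort of about 33 with early-childhood onset. Reporting them descriptively keeps them visible.
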